17.3.	Subject Identification, Enrollment, and Screening Logs	98
17.4.	Source Documentation	98
17.5.	Case Report Form Completion	99
17.6.	Data Quality Assurance/Quality Control	99
17.7.	Record Retention	99
17.8.	Monitoring	100
17.9.	Study Completion/Termination	100
17.9.1.	Study Completion/End of Study	100
17.9.2.	Study Termination	101
17.10.	On-Site Audits	101
17.11.	Use of Information and Publication	101
REFERENCES		103
INVESTIGATOR AGREEMENT		113
LIST OF ATTACHMENTS		
Attachment 1:	Toxicity Tables	106
Attachment 2:	Vaccination of Subjects From the Control Group With the Licensed Vaccine Nimenrix	110
Attachment 3:	Guidance on Study Conduct during the COVID-19 Pandemic	111

LIST OF IN-TEXT TABLES AND FIGURES

TABLES

Table 1:	Study Design VAC18194RSV2002.....	17
Table 2:	Summary of Immunogenicity Assays (Humoral)	20
Table 3:	Summary of Immunogenicity Assays (Cellular).....	20
Table 4:	Study Design VAC18194RSV2002.....	40
Table 5:	Summary of Immunogenicity Assays (Humoral)	65
Table 6:	Summary of Immunogenicity Assays (Cellular).....	66
Table 7:	Probability of Observing at Least One Adverse Event at a Given True Adverse Event Rate.....	76

FIGURES

Figure 1:	Schematic Overview of the Study.....	45
Figure 2:	Procedures in the Event of a Respiratory Tract Infection or Otitis Media Case	69

PROTOCOL AMENDMENTS

Protocol Version	Issue Date
Original Protocol	21 December 2017
Amendment 1	06 April 2018
Amendment 2	13 July 2018
Amendment 3	07 November 2018
Amendment 4	08 April 2019
Amendment 5	05 July 2019
Amendment 6	25 May 2020

Amendment 6 (Issued date: 25 May 2020)

The overall reason for the amendment:

This protocol amendment is made primarily to reduce the overall number of RSV-seronegative toddlers in the study from 48 to 36. The reduction is made because of difficulties in recruiting seronegative toddlers due to a higher than expected seropositivity rate in the 12-24 month age group.

The table below gives an overview of the rationale for each change and all affected sections

Rationale: To reduce the overall number of RSV-seronegative toddlers in the study from 48 to 36.

Synopsis: Overview of Study Design

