3.1 Overview of Study Design

11.2 Sample Size Determination

Rationale: Clarification that all concomitant medications utilized during an RTI or OM case will be collected, including outside of the 28-day post-vaccination period.

Synopsis: Safety Evaluations

Time and Events Schedule

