Attachment 3: Guidance on Study Conduct during the COVID-19 Pandemic

Amendment 5 (Issued date: 05 July 2019)**The overall reason for the amendment:**

This amendment is made to align the global protocol with changes made following requests from the German Health Authority:

- Clarification is added that the consent of both parents/legal guardians will be required in countries where this is specified by local regulation;
- Clarification is added on the reporting of any RTI or case of otitis media fulfilling the criterion of an SAE: all RTIs and cases of otitis media meeting seriousness criteria will be reported as SAEs; any RTI or case of otitis media reported as an (S)AE that is found to be positive for RSV will be excluded from the analyses of (S)AEs. However, the case will remain in the clinical database and will be tabulated separately in the clinical study report;
- Update of the monitoring rule for severe RSV-LRTI to reduce the numbers of events required to start an analysis from 3 to 2.

The table below gives an overview of the rationale for each change and all affected sections

Rationale: To clarify that in countries where local regulation requires that both parents/legal guardians give consent, this will be applicable.

*4.1 Inclusion Criteria**9.1.3.1 Screening Phase: Days -42 to 1**16.1 Study-Specific Design Considerations**16.2.3 Informed Consent**16.2.4 Privacy of Personal Data*

Rationale: To clarify the reporting of any RTI or case of otitis media fulfilling the criterion of an SAE.

*Synopsis: RTI Procedures**Time and Events Schedule**9.2.2 RTI Procedures**11.6 RSV Infection**11.7 Safety Analyses**12.1.1 Adverse Event Definitions and Classifications*

Rationale: Update of the monitoring rule for severe RSV-LRTI to reduce the numbers of events required to start an analysis from 3 to 2.

*Synopsis: Statistical Methods**11.3.1.3 Monitoring Rule for Severe RSV-LRTI*

Rationale: In addition, other minor changes, clarifications, and corrections were made throughout the protocol.

Amendment 4 (Issued date: 08 April 2019)

The overall reason for the amendment: To introduce more active follow-up of ongoing RTIs/otitis media cases to capture the potential worsening of RTI/otitis media cases that are reported as not severe during the initial RTI visit and to clarify the responsibilities of the CEC in terms of evaluation of RTI cases and severity grading of RTIs.

Updates and clarifications are made as specified below.

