3. STUDY DESIGN AND RATIONALE

3.1. Overview of Study Design

This is a multi-center, randomized, observer-blindⁱ, Phase 1/2a study, to be conducted in 36 male and female RSV-seronegative toddlers aged ≥ 12 to ≤ 24 months.

Each subject's RSV serostatus will be assessed by RSV enzyme immunoassay (EIA) at screening^j (see Section 9.1.3.1). *Note*: serostatus may be assessed via this assay if available from a different study of the sponsor (VAC18194RSV2001). If done within 42 days of first dose, this assessment would not have to be repeated in the absence of a history of respiratory infection during that period. Additionally, the seronegative status will be confirmed by the absence of an anamnestic humoral immune response (which is usually observed 7-10 days post antigen re-exposure in RSV seropositive subjects) from blood samples taken 7 days after the first dose.

ⁱ *Note*: The vaccine administrator will be unblinded but will have no other study function following dosing. The site staff or qualified professional staff who will do the observation and the subjects will be blinded.

^j The cut-off for seronegativity is a titer < 1 EIA unit.

Subjects will be randomized 1:1 to receive either Ad26/Ad26/Ad26 (at 2.5×10^{10} vp) or placebo/placebo/Nimenrix ^{k,1} (or placebo/placebo/placebo) (Table 4).

Table 4: Study Design VAC18194RSV2002

Group	N ^a	Day 1	Day 29/Week 4	Day 57/Week 8
RSV-seronegative toddlers 12 to 24 months				
Group 1	18	Ad26.RSV.preF (2.5×10^{10} vp)	Ad26.RSV.preF (2.5×10^{10} vp)	Ad26.RSV.preF (2.5×10^{10} vp)
Group 2	18	Placebo (saline)	Placebo (saline)	Nimenrix ^b or Placebo (saline)

N = number of subjects; vp = viral particles

^a: At the time of Amendment 6, 37 subjects have been enrolled.

^b: In countries where the commercial vaccine Nimenrix is licensed, placebo (0.9% saline) can be replaced with Nimenrix as the Day 57 vaccination for the study subjects in the control group, in accordance with the local label and local regulations, and unless contra-indicated. Nimenrix will be administered, only if permitted by the subject's parent/legal guardian and following PI assessment on a case-by-case basis as vaccination with Nimenrix outside this study might be preferred (joint parent/legal guardian and PI decision). In the US, Nimenrix will not be used unless it has been licensed for use or an Investigational New Drug (IND) has been submitted.

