- Assuming all subjects are recruited before the season, if 4 severe RSV-LRTI events are observed and all occur in the Ad26.RSV.preF group, enrollment in all pediatric studies with Ad26.RSV.preF will be halted and monitoring of all enrolled subjects will be increased (see Section 11.3.1.3).

Nimenrix has been shown to be at least as effective as comparable vaccines at stimulating an immune response to the 4 groups of the *N. meningitidis* bacterium in people of different age groups. Nimenrix offered the benefits of conjugated vaccines over conventional vaccines, including producing a strong immune response in young children. Nimenrix is well-tolerated and it can be safely given together with other routinely used vaccines in the different age groups.¹²

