11.2. Sample Size Determination

The number of subjects chosen for this study will provide a preliminary safety and immunogenicity assessment. Control recipients (Nimenrix or placebo) are included for blinding and safety purposes and will provide additional control specimens for immunogenicity assays.

While mild to moderate vaccine reactions (local site and systemic responses) are expected, AEs that preclude further dose administration or more serious ones that would limit product development are not anticipated.

[Table 7](#) shows the probabilities of observing at least 1 AE at given true AE rates:

Table 7: Probability of Observing at Least One Adverse Event at a Given True Adverse Event Rate

True Adverse Event Rate	Probability of Observing at Least One Adverse Event in N Subjects	
	N=18	
0.5%	9%	
1%	17%	
2.5%	37%	
5%	60%	
10%	85%	
25%	99%	
50%	100%	

A monitoring rule for severe RSV-LRTI is described in Section 11.3.1.3. Based on this rule and assuming an event rate in controls of 1%, there is at least 80% power to halt enrollment in this or the next study if the incidence in the Ad26.RSV.preF group is approximately 25% or more.

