11.3.1.3. Monitoring Rule for Severe RSV-LRTI

In this section ‘severe RSV-LRTI’ refers to the assessment made by the CEC.

With respect to the secondary endpoint ‘severe RSV-LRTI’, a monitoring rule for severe RSV-LRTI is as follows.

- If 1 event (regardless of group) of ‘severe RSV-LRTI’ is observed, no analysis will be done. *Note:* However, the IDMC will be informed and may convene.
- As soon as 2 or more events (regardless of group) of ‘severe RSV-LRTI’ have been observed, confidence limits for the difference in proportions (using Wilson score method) between the Ad26.RSV.preF group and control group (pooling placebo/placebo/Nimenrix and placebo/placebo/placebo) will be constructed by the external statistician who is supporting the IDMC:
 - If the upper (one-sided) 95% confidence limit for the difference is $<10\%$: continue the study; if study enrollment is still ongoing, continue enrollment.
 - If the upper (one-sided) 95% confidence limit is $\geq 10\%$ and the lower (one-sided) 80% confidence limit is >0 : more frequent active monitoring of subjects, including weekly calls within the RSV season and more frequent medical review will be initiated.
 - If the upper (one-sided) 95% confidence limit is $\geq 10\%$ and the lower (one-sided) 95% confidence limit is >0 : halt enrollment in this study or the next study; more frequent active monitoring of subjects, including weekly calls within the RSV season and more frequent medical review for all enrolled subjects should be initiated.

For example: assuming complete enrollment, if 2 or 3 severe RSV-LRTI events are observed and all occurred in the Ad26.RSV.preF group, the lower (one-sided) 80% (but not the 95%)

confidence limit will be >0 and monitoring will be increased. If 4 severe RSV-LRTI events are observed and all occurred in the Ad26.RSV.preF group, the lower (one-sided) 95% confidence limit will be >0 and enrollment in all pediatric studies with Ad26.RSV.preF will be halted and monitoring of all enrolled subjects will be increased.

More details on this monitoring rule are specified in the IDMC charter.

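### At 18 per arm, three severe RSV-LRTI events against none already meet the halt rule; the worked example says they do not

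*Protocol*

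**What the plan says.** Protocol 11.3.1.3 compares the Ad26.RSV.preF group with the pooled control group once two or more severe RSV-LRTI events have occurred. Increased monitoring follows if the upper one-sided 95% limit is at least 10% and the lower one-sided 80% limit is above zero. A halt follows if the upper condition holds and the lower one-sided 95% limit is above zero.

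The section then illustrates the rule, taking enrollment as complete, with this case: "if 2 or 3 severe RSV-LRTI events are observed and all occurred in the Ad26.RSV.preF group, the lower (one-sided) 80% (but not the 95". In other words, the 80% limit is above zero, the 95% limit is not, and only monitoring increases. Four events, all in the vaccine group, are given as the halting case. The Synopsis repeats this. Section 3.3.5 also uses four: "if 4 severe RSV-LRTI events are observed and all occur in the Ad26.RSV.preF group, enrollment in all pediatric studies" with the vaccine will be halted.

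Section 11.2 says that, with 1% in controls, the rule has "at least 80% power to halt enrollment in this or the next study if the incidence in the Ad26.RSV.preF group is approximately 25" (per cent, or higher).

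On size, 3.1 describes a study "to be conducted in 36 male and female RSV-seronegative toddlers aged" 12 to 24 months, 18 per group, and a footnote to Table 4 adds: "At the time of Amendment 6, 37 subjects have been enrolled". Amendment 6 was made primarily to "reduce the overall number of RSV-seronegative toddlers in the study from 48 to 36".

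**The concern.** The example is the only place where the protocol turns the confidence-limit rule into event counts. If it misplaces 3/0, a reader expects enrollment to continue in a case where the rule calls for a halt. The rule watches for a first sign of enhanced respiratory disease, and the example says that a halt extends to all pediatric studies of the vaccine.

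The example and 11.2 also cannot both describe the same rule at 18 per arm, because the stated power depends on whether 3/0 halts.

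The amendment history suggests how this arose. Amendment 5 lists 11.3.1.3 as changed ("Update of the monitoring rule for severe RSV-LRTI to reduce the numbers of events required to start an analysis from 3 to 2") while the planned total was still 48. For the cut to 36, Amendment 6 lists the Synopsis design overview, 3.1 and 11.2, but not 11.3.1.3. That the example was not recomputed is an inference; the arithmetic below does not depend on it.

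**Working it through.** **Inputs**
- Arm sizes: 18/18 (Protocol 3.1, Table 4); formerly 24/24 (total of 48, Amendment 6).
- Method: Wilson score limits for a difference (11.3.1.3). SAP 5.2 cites a paper comparing intervals for a difference between two independent proportions. I read this as Newcombe's combination of two Wilson intervals. No continuity correction is mentioned, so none is applied.
- z = 1.6449 (one-sided 95%) and 0.8416 (one-sided 80%).
- Power inputs: control 1%, vaccine 25% (11.2).

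**Formulas**

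Wilson limits for one arm, with p = x/n:

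l, u = [p + z²/(2n) ∓ z√(p(1−p)/n + z²/(4n²))] / (1 + z²/n)

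Limits for the difference (arm 1 vaccine, arm 2 control):

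L = (p₁−p₂) − √[(p₁−l₁)² + (u₂−p₂)²]

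U = (p₁−p₂) + √[(u₁−p₁)² + (p₂−l₂)²]

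**Step 1. Reproduce the example at the former size, 24/24**

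| Events (vaccine/control) | Lower 80% | Lower 95% | Action |
|---|---|---|---|
| 2/0 | +0.0370 | −0.0321 | increase monitoring |
| 3/0 | +0.0706 | −0.0004 | increase monitoring |
| 4/0 | +0.1053 | +0.0314 | halt |

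The example is exactly right here.

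**Step 2. The planned size, 18/18**

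For 3/0 at z = 1.6449: p₁ = 0.1667, l₁ = 0.0686, u₁ = 0.3518; p₂ = 0, l₂ = 0, u₂ = 0.1307.

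- L = 0.1667 − √(0.0980² + 0.1307²) = +0.0033
- U = 0.1667 + (0.3518 − 0.1667) = 0.3518

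| Events | Lower 80% | Lower 95% | Upper 95% | Rule gives | Example says |
|---|---|---|---|---|---|
| 2/0 | +0.0498 | −0.0389 | 0.2864 | increase monitoring | increase monitoring |
| 3/0 | +0.0949 | +0.0033 | 0.3518 | **halt** | increase monitoring |
| 4/0 | +0.1417 | +0.0460 | 0.4131 | halt | halt |

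With equal arms, the 3/0 lower 95% limit is above zero at every n from 12 to 22 and below zero from 23 to 30.

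**Step 3. Power**

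P(halt) is the sum of the two binomial probabilities over all outcomes with at least 2 events, L95 > 0 and U95 ≥ 0.10.

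- 18/18, rule as written: 79.7%; 80% is reached at a vaccine incidence of about 25.2%. This reproduces 11.2.
- P(exactly 3/0) = C(18,3)·0.25³·0.75¹⁵ × 0.99¹⁸ = 0.1704 × 0.8345 = 14.2%.
- 18/18 if 3/0 does not halt: 79.65% − 14.22% = 65.4%; 80% is reached only at about 30%.
- 24/24: 84.8%, with 3/0 not halting. The power sentence alone therefore does not show whether it was revised for the smaller study.
- 18/18 with 1% in both arms: the false-halt probability is 0.06% when 3/0 halts.

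**Step 4. Sensitivity to the split**

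The documents do not say how the 37 enrolled subjects divide.

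| Vaccine/control | 3/0 lower 95% | 3/0 halts? | Power at 25% |
|---|---|---|---|
| 18/19 | +0.0081 | yes | 79.5% |
| 19/18 | −0.0025 | no | 69.8% (80% at about 28.5%) |
| 18/17 | −0.0020 | no | 65.7% |
| 17/18 | +0.0097 | yes | 76.6% |

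**The case against.** - **The enrolled number is 37, not 36.** At 19 vaccine/18 control the example is true, and editing it to fit 18/18 would put an error into correct text. This stands, and it makes the fix conditional on the split. It does not clear the protocol: at 19/18 the power falls to 69.8%, so 11.2 would be wrong instead.
- **The denominator is not named.** Section 11.1 makes the mITT set primary for RSV infection, and 11.3.1.3 does not say which set the rule uses. One subject fewer in an arm can move 3/0 either way. This stands as a further reason to tabulate cases; the example itself assumes complete enrollment.
- **A continuity correction rescues the example at 18/18.** The corrected limits are 2/0 lower 80% +0.0043, 3/0 lower 95% −0.0424 and 4/0 lower 95% +0.0002. But no document mentions a correction, it gives only 62.3% power against the 80% stated, and at 24/24 it fails the example (4/0 lower 95% −0.0038). The IDMC charter, which holds further detail on the rule, was not available.
- **The illustration decides nothing.** The external statistician computes the limits and the IDMC makes a recommendation from unblinded data. The enrollment target has been reached, and both tiers increase monitoring in the same way. This limits the consequence and stands. A wrong count beside a stopping rule still needs correcting, because protocol readers will take it as the threshold.

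**Conclusion.** The example is wrong as written at the protocol's planned size. Under uncorrected Newcombe–Wilson limits with 18 per arm, 3/0 meets both halt conditions (lower +0.0033, upper 0.352). The smallest halting case with no control events is therefore three, not four. The margin is thin, 0.33 percentage points, but the rule is a strict test against zero.

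The statements about 2/0 and 4/0 are true, and so is the sentence in 3.3.5, although it implies that four is the threshold. At 18/18 the power sentence in 11.2 holds (79.7%) only if 3/0 halts; following the example gives 65.4%.

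The rule itself is unaffected. The practical consequence is mainly whether the next or other pediatric studies are halted at 3/0. The pausing rules in 11.10 also act, but they are not specific to RSV disease. The conclusion rests on there being no continuity correction and on 18/18. At both possible near-equal splits of the 37, it changes only which text needs correcting: the example at 18 vaccine/19 control, the power sentence at 19/18. It should be fixed.

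**What to change.** 1. Establish the actual split and the analysis set used for the rule, then recompute the example and the 11.2 power together.
   - At 18/18: in 11.3.1.3 and the Synopsis, increased monitoring applies to 2 events and the halt to 3 or more, with none in controls. Align 3.3.5.
   - At 18 vaccine/19 control: make the same change and give the power as 79.5% at 25%.
   - At 19 vaccine/18 control: keep the example and restate the power as about 70% at 25%, with 80% reached at about 28.5%.
2. State the interval method in full, including that no continuity correction is used.
3. State that the computed limits govern and the example is only illustrative.
4. Put a small lookup table of event splits and resulting actions in the IDMC charter. At 18/18 the smallest halting cases are 3/0, 5/1, 7/2 and 8/3.

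The cost is wording in three protocol sections, a rechecked power figure in 11.2 and a short table, with no new data or subjects. If the split is 19/18, the sponsor must report a less favourable power.

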11.3.2. Definitions of RSV MA-RTI

RSV MA-RTI includes all subjects with RSV-RTI that is medically-attended, ie, when the subject's parent/legal guardian or caregiver seeks medical attention outside normal study procedures, including healthcare professional visits to the home, clinic visits, emergency room attendance, and hospital admission.

Determination of RSV Infection

A subject is considered RSV positive if the subject has a positive RT-PCR for RSV nasal (mid-turbinate or nasopharyngeal) samples (central laboratory; see Section 9.2.2). If no central laboratory RT-PCR result is available, a positive test result (including commercial test results) for RSV from a local laboratory (if available) could be used to confirm RSV infection upon evaluation by the CEC.

If a test result for RSV is missing (ie, not available or not conclusive), the RTI will not be considered RSV-related.

11.4. Subject Information

For all subjects, demographic characteristics (eg, age, weight and length percentiles according to WHO pediatric growth and weight charts,⁴⁹ race, and gender), and other baseline characteristics (eg, physical examination, medical history, concomitant diseases) will be tabulated and summarized with descriptive statistics.

11.5. Immunogenicity Analyses

No formal hypothesis on immunogenicity will be tested. Descriptive statistics (geometric mean and 95% confidence interval for ELISA and virus neutralization assays; median and quartiles for ELISpot and ICS) will be calculated for continuous immunologic parameters at all timepoints. Graphical representations of immunologic parameters will be made as applicable.

Frequency tabulations will be calculated for discrete (qualitative) immunologic parameters as applicable.

The primary analysis set for immunogenicity is the PPI set. As a sensitivity analysis, key tables will also be based on the FA set. Depending on their occurrence, the effect of missed doses or natural infections might be further explored. Note that they will be included in the tables showing the FA set.

11.6. RSV Infection

The presence of RSV infection, as described in Section 9.2.2, will be assessed by RT-PCR. The presence of RSV infection will be summarized by descriptive statistics.

Any RTI or otitis media case recorded as an AE in the eCRF that is subsequently found to be RSV positive by RT-PCR (central laboratory or based on CEC assessment if available) will be excluded from the safety analysis and tabulated separately (refer to Section 11.7).

The mITT set is the primary analysis set for assessment of RSV infection in seronegative subjects.

11.7. Safety Analyses

No formal statistical testing of safety data is planned. All safety data will be analyzed descriptively by regimen.

Adverse Events

The verbatim terms used in the eCRF by investigators to identify AEs will be coded using the Medical Dictionary for Regulatory Activities (MedDRA). All reported AEs with onset after vaccination up to 28 days post-vaccination, and SAEs from first dose administration onwards, will be included in the analysis. For each AE, the percentage of subjects who experience at least 1 occurrence of the given event will be summarized by group.

Summaries, listings, datasets, or subject narratives may be provided, as appropriate, for those subjects who die, who discontinue vaccine due to an AE, or who experience a severe AE or an SAE.

Summaries and/or listings may be provided separately for AEs with onset outside the above defined time frame (eg, beyond 28 days post-vaccination) and that were reported pre-dose at the moment of subsequent vaccinations for studies using multiple doses.

Solicited local (at injection site) and systemic AEs will be summarized descriptively. The overall frequencies per vaccine group as well as frequencies according to severity and duration will be calculated for solicited AEs. In addition, the number and percentages of subjects with at least one solicited local (at injection site) or systemic AE will be presented. Frequencies of unsolicited AEs, separately for all and vaccination-related only, will be presented by System Organ Class and preferred term. *Note*: Frequencies of post-dose 3 AEs in the control group will be presented separately for Nimenrix and placebo.

Any RTI or otitis media case recorded as an AE in the eCRF that is subsequently found to be RSV positive by RT-PCR (central laboratory or based on CEC assessment if available) will be excluded from the safety analysis and tabulated separately.

Vital Signs

A tabulation of the distribution of temperatures per half degree intervals will be provided. For heart rate and respiratory rate, the percentage of subjects with values beyond clinically relevant limits will be summarized. *Note:* Vital signs data post-dose 3 in the control group will be presented separately for Nimenrix and placebo.

Physical Examination

Physical examination abnormalities will be listed.

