3.2. Study Design Rationale

Vector Selection

The rationale behind the selection of the Ad26 vector is described in Section 1.1.

Dose Selection

In study VAC18194RSV2001, ongoing in UK and Finland, the IDMC reviewed the interim analysis when 12 toddlers had reached Day 8 post-first dose (5×10^{10} vp of Ad26.RSV.preF or placebo). Their recommendation was that the study should continue unmodified. Transient fevers were observed in some subjects, comparable in intensity to those seen following measles, mumps and rubella (MMR) immunization in this age group. A recent study from Africa in 1- to 3-year-old infants revealed only 5 cases of fever in over 380 subjects in which 2/3 infants had received 5×10^{10} vp of an Ad26-vectored Ebola vaccine. Thus, the transient fevers observed in study VAC18194RSV2001 may be based on a regional effect. In addition, available immunogenicity data from study VAC18194RSV2001 in 8 toddlers after the first dose (5 after 5×10^{10} vp of Ad26.RSV.preF and 3 after placebo) showed that the vaccine was immunogenic, inducing a consistent increase in neutralizing antibody titers without affecting qualitative Th1/Th2 balances. Prior to dosing toddlers in the current study (VAC18194RSV2002), the IDMC will convene to review additional safety data (unblinded at the study group level) from VAC18194RSV2001 collected up to this point (from at least the first 12 toddlers), including solicited AEs, unsolicited AEs and SAEs through 28 days after the first dose of 5×10^{10} vp of Ad26.RSV.preF; immune response data (RSV F protein binding antibodies [pre-F and/or post-F], RSV virus neutralization assay, and Th1/Th2 subtyping) through 28 days after the first dose are also expected to be available for additional toddlers dosed in VAC18194RSV2001. The continued general safety and tolerability of the vaccine in VAC18194RSV2001 will further support the expectation that safety will be acceptable at the dose of 2.5×10^{10} vp in the current study.

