5. STUDY VACCINE ALLOCATION AND BLINDING

Study Vaccine Allocation

Central randomization will be implemented in this study. Subjects will be randomly assigned to a treatment group based on a computer-generated randomization schedule prepared before the study by or under the supervision of the sponsor. The randomization will be balanced by using randomly permuted blocks. No stratification will be applied.

The randomization ratio is 1:1.

The interactive web response system (IWRS) will assign a unique code, which will dictate the group assignment for the subject. The requestor must use his or her own user identification and personal identification number when contacting the IWRS, and will then give the relevant subject details to uniquely identify the subject.

If randomized subjects are withdrawn from vaccination before the first dose is administered, additional subjects may be recruited to replace these subjects at the discretion of the sponsor. Any replacement subject will be assigned to the same group as the original (discontinued) subject. The replacement subject's randomization number will equal the randomization number of the discontinued subject +1000 (for example subject 0001 would be replaced by subject 1001). These additional subjects should also be randomized through IWRS.

Any randomized subject who is withdrawn from the study for reasons other than due to an AE after the first dose but before the second dose might be replaced at the discretion of the sponsor. Any replacement subject will be assigned to the same group as the original (discontinued) subject. The replacement subject's randomization number will equal the randomization number of the discontinued subject +2000.

Every effort will be made to determine the serostatus of subjects. During the study, any subject who was assessed as seronegative at screening and who subsequently shows an anamnestic response at Day 8 will be replaced if possible.

Blinding

The investigator will not be provided with randomization codes until the final analysis is performed. The codes will be maintained within the IWRS, which has the functionality to allow the investigator to break the blind for an individual subject.

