## 4. SAFETY

Continuous variables will be summarized using the following statistics, as appropriate: number of observations, arithmetic mean (mean), 95% CI for the mean, standard deviation (SD), standard error (SE), median, quartiles (Q1 and Q3), minimum and maximum. Frequencies and percentages (to one decimal place) will be generated for categorical variables.

Safety data will be summarized in each period of the active phase. Only SAEs will be tabulated for all phases, including the non-active phases. The analysis phases are defined in section 2.1. Denominator for the percentages is the number of subjects in the considered population and period for a certain regimen (incidence per 100 subjects/period).

*Note:* Safety data post-dose 3 in the control group will be presented separately for Nimenrix and placebo, unless otherwise specified (section 5.2).

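### No pooled control column is specified for post-dose 3 AEs and vital signs, so the planned dose 3 displays set the vaccine group against two non-randomised control subsets

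*Protocol*

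**What the plan says.** **Allocation.** Protocol Section 3.1: "Subjects will be randomized 1:1 to receive either Ad26/Ad26/Ad26" or the control regimen. Table 4 shows the controls as one group of 18, with Nimenrix or saline as alternatives on Day 57. Section 5 adds: "No stratification will be applied".

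**Who gets Nimenrix.** Section 3.1, Table 4 footnote: "In countries where the commercial vaccine Nimenrix is licensed, placebo (0.9% saline) can be replaced with Nimenrix as the Day 57 vaccination". This is subject to local label, local regulations and contraindications, and is finally a "joint parent/legal guardian and PI decision". Attachment 2 adds the child's age and the childhood vaccines already received.

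**Post-dose 3 display.** Protocol Section 11.7: "Frequencies of post-dose 3 AEs in the control group will be presented separately for Nimenrix and placebo". A second note in that section says the same for vital signs. SAP Section 4: "Safety data post-dose 3 in the control group will be presented separately for Nimenrix and placebo, unless otherwise specified (section 5.2".

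**Where controls are pooled.** SAP Section 5.2 and Protocol Section 11.3.1.3 pool the two control sequences for the severe RSV-LRTI monitoring rule. No passage specifies pooling for post-dose 3 AEs or vital signs.

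**The concern.** Protocol Section 3.2 gives the controls, Nimenrix and saline together, the job of showing what happens without Ad26.RSV.preF, and relies on randomisation to balance the groups. After dose 3, only the control group as a whole rests on that randomisation. Each subset is picked out by country and by decisions made case by case, while the vaccine group is not divided in the same way. A difference between all vaccinees and the saline controls can then reflect who ended up in the saline subset as well as the vaccine.

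Safety of the three-dose regimen is the primary objective, and the SAP summarises safety by post-dose period, so dose 3 is one of three such displays. The split also leaves smaller control columns in an already small trial.

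**Working it through.** **1. Inputs.** Controls: n = 18 (Protocol Table 4; its footnote says 37 children were already enrolled at Amendment 6, so the actual number may differ slightly). The number given Nimenrix is not stated. I assume a subset of k = 3 to 15 of the 18.

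**2. Reproduce the plan's own figures.** Protocol Table 7 gives the probability of at least one AE in 18 subjects, which is 1 − (1 − p)^18.

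| True rate | 0.5% | 1% | 2.5% | 5% | 10% | 25% | 50% |
|---|---|---|---|---|---|---|---|
| Table 7 | 9% | 17% | 37% | 60% | 85% | 99% | 100% |
| Recomputed | 8.63% | 16.55% | 36.60% | 60.28% | 84.99% | 99.44% | 100.00% |

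Table 7 reproduces throughout.

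**3. The same formula in a split column.** At p = 10%, 1 − 0.9^k. For example, k = 9 gives 1 − 0.3874 = 61.3%. The last column illustrates precision with assumed rates: vaccine 9/18 against one third in the control column, two-sided 95% Newcombe interval. No such interval is planned for AEs.

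| Controls in column | Weight of one event (1/k) | P(at least one AE), p = 10% | 95% CI for difference (points) |
|---|---|---|---|
| 18 (pooled) | 5.6 points | 85.0% | −14.4 to 43.7 |
| 15 | 6.7 | 79.4% | −15.9 to 44.4 |
| 12 | 8.3 | 71.8% | −18.0 to 45.3 |
| 9 | 11.1 | 61.3% | −21.0 to 46.5 |
| 6 | 16.7 | 46.9% | −25.6 to 48.3 |
| 3 | 33.3 | 27.1% | −33.8 to 51.0 |

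The interval takes the Wilson limits (l, u) of each proportion. With d = p1 − p2, its lower limit is d − √[(p1 − l1)² + (u2 − p2)²] and its upper limit is d + √[(u1 − p1)² + (p2 − l2)²]. For the first row, 9/18 has Wilson limits 29.0% and 71.0%, and 6/18 has 16.3% and 56.3%. The lower limit is 16.7 − √(21.0² + 22.9²) = −14.4 points; the upper is 16.7 + √(21.0² + 17.1²) = 43.7 points (unrounded limits used).

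**4. What can be recovered from the split columns.** Each child dosed on Day 57 receives one product, so the subsets are disjoint and together make up the post-dose 3 control group. With a of n1 and b of n2 subjects affected, the pooled proportion is (a + b)/(n1 + n2). This covers AE frequencies, half-degree temperature counts and counts beyond the vital-sign limits. It does not cover everything: SAP Section 4.2 summarises heart rate, respiratory rate and SpO2 with descriptive statistics, and SAP Section 4 lists the median and quartiles among these. Pooled medians and quartiles cannot be computed from two sets of subset medians and quartiles.

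**The case against.** The strongest reply is that nothing is really lost. Protocol Section 11.7 also promises AE percentages by group and overall solicited AE frequencies per vaccine group, neither limited to doses 1 and 2. The split can be read as an addition to those summaries, and the pooled AE proportion is a sum away. This largely stands for AE counts. It falls short in that the notes on dose 3 are specific where the other sentences are general, an all-dose summary does not show dose 3, and medians and quartiles cannot be summed.

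Second, the detailed plan is not in view. The SAP supplied covers the IDMC analyses, its one planned analysis is at Day 8 after dose 1 in the first 12 toddlers, and table layouts sit in a separate specification. This stands: the columns of the primary and final analysis tables are unknown.

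Third, the split is sensible. Protocol Section 3.3.3 lists fever, irritability, loss of appetite and injection-site reactions as common after Nimenrix, and these overlap the solicited events. A pooled rate depends on the unplanned Nimenrix share: with assumed rates of 10% after saline and 30% after Nimenrix, shares of 25%, 50% and 75% give 15%, 20% and 25%. This is a reason to keep the split, not to omit the total.

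Fourth, safety is descriptive, with no formal testing, so no alpha or power is lost. That is correct; the cost is in interpretation.

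A reader might go further and infer that the randomised dose 3 comparison will never be shown. The documents do not say so: neither note says the split is the only display, and nothing excludes a pooled one. A reader might also infer that regional fever differences will bias the split columns, since Protocol Section 3.2 says "the transient fevers observed in study VAC18194RSV2001 may be based on a regional effect". That sentence is a conjecture about another study at a higher dose, set against an Ebola-vaccine study in Africa. The documents do not list this study's countries or show that fever differs between them.

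**Conclusion.** The point holds as a gap in specification. For post-dose 3 AEs and vital signs the plan specifies the control group in two parts, formed by licensing, label, parent permission and investigator judgment. It specifies no display of the control group as a whole, so the comparisons it does specify are not the randomised contrast.

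The importance is minor. Doses 1 and 2 are unaffected because all controls receive saline, severe RSV-LRTI is already pooled, and AE counts can be added by hand. The loss of resolution in a single column depends wholly on the unknown split: at a 10% true rate, 27% to 79% for the assumed 3 to 15 children, against 85% for 18. Those figures assume that all 18 planned controls receive dose 3. They describe the split columns alone and cease to matter once a total is printed.

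**What to change.** In the post-dose 3 AE and vital-sign tables, add a pooled control column, defined as all control subjects who received dose 3, beside the Nimenrix and saline columns. Keep the split columns.

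Footnote the pooled column to say that it mixes an active vaccine and saline, and give the number of children contributing from each. Because Protocol Section 11.1 assigns subjects as treated and the column covers only children who reached dose 3, its definition should say so instead of calling it simply as randomised. State the same in Protocol Section 11.7, in SAP Section 4 and in the SAP for the primary and final analyses, if it is not already there.

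The cost is one column per table. No new data are needed: the protocol already has the Day 57 product recorded for each child, and the monitoring rule already pools the controls.
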